### 10.6.3. Handling of Partial Dates

Element	Reporting Detail
General	
 
Partial dates will be displayed as captured in participant listing displays.
 

Adverse Events	
 
The eCRF does not allow partial dates to be captured for AEs. All dates will either be complete or missing.
 
Completely missing start or end dates will remain missing, with no imputation applied.
 
Where AE onset dates are missing then the AE will be considered on-treatment.
 

Concomitant Medications	
 
The eCRF allows partial dates to be captured for concomitant medications.
 
Partial dates for any concomitant medications recorded in the eCRF will be imputed using the following convention: 
 
If the partial date is a start date, a '01' will be used for the day and 'Jan' will be used for the month
 
If the partial date is a stop date, a '28/29/30/31' will be used for the day (dependent on the month and year) and 'Dec' will be used for the month.
 
 
 

Element	Reporting Detail
	

• The answers to the questions "Taken Prior to Study?" and "Ongoing?" which are recorded in the eCRF will also be taken into consideration to determine if the medication was started pre-treatment or continued post-treatment. In each case, should the answers suggest a different classification than the dates, the medication will be summarized in all possible classifications (pre-/during/post-treatment) in which it could conceivably have been taken.

Exacerbations	

• Exacerbations are treated in the same way as AEs.

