#### **9.2.6.1. Asthma Exacerbations**

For the purposes of this study, severe asthma exacerbations will be collected and recorded on the asthma exacerbation eCRF page from the start of treatment until follow up/or the EW visit for those subjects that withdraw from participation in the study.

A severe asthma exacerbation is defined as deterioration of asthma requiring the use/additional use of systemic corticosteroids (tablets, suspension, or injection), or antibiotics and inpatient hospitalisation, or emergency department visit due to asthma that required systemic corticosteroids or antibiotics. Further clarification will be present in the SRM.

Asthma exacerbations should not be recorded as an AE unless they meet the definition of an SAE.

These events will be recorded on the DRE page in the subject's eCRF within 24 hours of the physician becoming aware. The time period for collection of exacerbation information in the eCRF will be from the time that the ICF is signed until the Exit visit or EW.

For consistency, exacerbations separated by less than 7 days will be treated as a continuation of the same exacerbation.

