
Missing onset or resolution dates will be handled as follows:
 
 
Single event with missing onset and/or resolution dates: 
 
(a) Missing onset date: set onset date = study treatment start date
 
(b) Missing resolution date: set resolution date = study treatment stop date
 
(c) Both missing: imputed per both (a) and (b)
 
 
 
Multiple events, one event with some missing onset/resolution dates; on the assumption any partial date information does not occur during the other events: 
 
(a) Missing onset date: set onset date = max[(resolution date of the nearest previous event) + 1 day, study treatment start date]
 
(b) Missing resolution date: set resolution date = min[(onset date of the nearest subsequent event) - 1 day, study treatment stop date]
 
(c) Both missing: determine the largest gap between study treatment start date and first event onset date, between first event resolution date and next event(s) onset dates (if any), between last event resolution date and study treatment stop date. If there is more than one gap which is the largest, then take the first occurrence. Then impute as follows:  <math display="block">\text{onset date} = (\text{onset date of largest gap}) + 1 \text{ day}</math> <math display="block">\text{resolution date} = (\text{resolution date of largest gap}) + 1 \text{ day}</math> 
 
 
 

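### The SAP gives conflicting rules for undated severe exacerbations, and one of its imputation formulas ends the imputed event a day or two too late

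*SAP*

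**What the plan says.** Four places in the SAP bear on a severe exacerbation with a missing date.

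- **SAP 10.6.3 (Handling of Partial Dates).** The row for exacerbations reads "Exacerbations are treated in the same way as AEs". The adverse-event row says "Completely missing start or end dates will remain missing, with no imputation applied", and then "Where AE onset dates are missing then the AE will be considered on-treatment".
- **SAP 10.5.3.3 (Severe Asthma Exacerbations).** This block does impute. For a single event: "Missing onset date: set onset date = study treatment start date"; a missing resolution takes the treatment stop date. For several events, a missing onset becomes the later of the day after the previous resolution and the study treatment start date. For a missing resolution, the rule is to "set resolution date = min[(onset date of the nearest subsequent event) - 1 day, study treatment stop date". If both dates are missing, the programmer must "determine the largest gap between study treatment start date and first event onset date, between first event resolution date and next event(s) onset dates" and so on to treatment stop. The imputed event then runs from one day after the gap begins to one day after the gap ends.
- **SAP 7.3.2.2.** The annualised rate is the number of exacerbations divided by years on Relvar/Breo since randomisation, for on-treatment events, with no exclusion for missing dates.
- **SAP 10.8.6 (note to Table 2.23) and the EFF_T15 shell in Appendix 9.** Duration and annual rate use only events with both onset and resolution dates, and the footnotes require those dates to come from the eCRF.

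SAP 10.3.1.2 assigns study phase from the onset date alone. Protocol 9.2.6.1 adds that "exacerbations separated by less than 7 days will be treated as a continuation of the same exacerbation"; the SAP does not repeat this.

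**The concern.** SAP 10.5.3.3 and 10.6.3 give opposite instructions for the same data item, and neither refers to the other. The missing-data table in SAP 10.6.2 points to the governing section for rescue-free days, ACT and other PROs, but has no entry for exacerbations. Two programmers could each follow the SAP faithfully and build different exacerbation datasets. The Table 2.23 note adds a third treatment that does not match the rate definition in SAP 7.3.2.2.

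The outputs at stake are the annualised rate of severe exacerbations (an exploratory endpoint in Protocol Section 4), the numbers of events and of participants with an event, and the incidence of subjects with a severe exacerbation (a safety endpoint in Protocol 11.4.2). The both-missing formula in SAP 10.5.3.3 also disagrees with the neighbouring missing-resolution rule about which side of the next event's onset the imputed event should end.

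**Working it through.** The documents give no figure on this point to reproduce. The check applies the written rules to hypothetical histories. All event days below are assumptions; day 1 is randomisation and treatment stops on day 168 unless stated.

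**Study phase.** SAP 10.3.1.2 makes an onset before randomisation run-in, an onset up to treatment stop + 1 day on-treatment, and a later onset post-treatment.

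| Undated onset | SAP 10.6.3 | SAP 10.5.3.3 |
|---|---|---|
| Single event, treatment start read as randomisation (day 1) | on-treatment | day 1: on-treatment |
| Single event, treatment start read as run-in start (day -28) | on-treatment | day -28: run-in |
| Previous event resolved day 105, treatment stop day 100 | on-treatment | day 105 + 1 = 106, later than 100 + 1 = 101: post-treatment |

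The two sections agree in the first case and differ in the other two.

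**Count.** Take dated events on days 30–40 and 100–110, and a third event with both dates missing.

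1. Gaps: 1 to 30 (29 days), 40 to 100 (60 days), 110 to 168 (58 days). The largest is 40 to 100.
2. Imputed event under 10.5.3.3: onset 40 + 1 = 41, resolution 100 + 1 = 101.
3. Under 10.6.3 the undated event simply counts, giving 3 events. Under 10.5.3.3 without merging there are also 3.
4. If the protocol's 7-day rule is applied to the imputed dates, day 41 is 1 day after day 40, and day 100 falls inside the imputed event. All three merge into 1.

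**Rate.** Time on treatment is 168/365.25 = 0.460 years.

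- All three events counted (SAP 7.3.2.2): 3/0.460 = 6.52 per year.
- Undated event excluded (Table 2.23 note): 2/0.460 = 4.35 per year.
- Imputed, then merged: 1/0.460 = 2.17 per year.

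**The both-missing formula.** If the gap ends at a following event with onset day d, the imputed resolution is d + 1. The shared days are d and d + 1, so the overlap is (d + 1) - d + 1 = 2 days. In the example, days 41–101 overlap days 100–110 on days 100 and 101. The neighbouring rule uses d - 1, which would give days 41–99 and no overlap.

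If the largest gap is the last one, nothing follows. With one dated event on days 10–20, the gap is 20 to 168 and the imputed event is days 21–169, which ends one day after treatment stop. The neighbouring rule caps at the stop date.

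Changing the sign in the three-event example leaves the onset at day 41, the phase on-treatment, and the merged count at 1. Only the imputed resolution, and hence the imputed duration, moves.

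**The case against.** Several stronger conclusions are tempting, and the documents do not support them.

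- **A reader might infer that the + 1 day changes the count or the phase.** It does not. Phase depends on onset only, and the merged count is the same with either sign. The overlap also requires a following event, and the single-event both-missing rule has no such problem.
- **A reader might infer that an event without an onset date is always moved into run-in**, because SAP 10.3.1 says participants take Relvar/Breo from run-in. But SAP 10.5.1, under the heading on study treatment start and stop dates, defines the on-treatment start as the randomisation date, and SAP 10.5.2 repeats this. On that reading a single event is on-treatment under both rules. What remains is an undefined term in 10.5.3.3.
- **A reader might infer that imputation itself turns three events into one.** That needs the 7-day rule to be applied to imputed dates. The rule is in the protocol, and the SAP does not say so. An onset imputed alone need not follow the previous event by one day either, since it can default to treatment start.
- **A reader might infer that the choice would be made after seeing results.** SAP Section 3 describes pre-programming on scrambled data, and Table 2.23 is a dry-run deliverable. The choice could be settled before unblinding, although the SAP does not settle it.

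It can also be argued that the Table 2.23 restriction keeps events without eCRF dates out of the rate whether or not they are imputed. That is correct for the display, but it conflicts with SAP 7.3.2.2 and does not govern the numbers of events and participants. The contradiction between 10.5.3.3 and 10.6.3 stands, as does the mismatch inside 10.5.3.3.

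**Conclusion.** The SAP cannot be followed as written for severe exacerbations with missing dates, because two sections conflict without precedence and a third instruction conflicts with the rate definition. The consequences are conditional:

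- phase differs if treatment start means run-in start, or if an earlier event resolved after treatment stop;
- the count differs if imputed dates enter the 7-day merge;
- the rate differs if undated events are excluded.

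The + 1 day is a separate, smaller error confined to the imputed resolution date.

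The effect on the trial is small. The summaries are exploratory or safety summaries and descriptive. The threefold spread in rate is for one constructed participant, not an arm. The documents do not say how many undated events there are, so no arm-level effect can be estimated.

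**What to change.** Keep one rule and cross-refer to it from the other section.

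- **Simplest:** delete the date imputation in SAP 10.5.3.3 and apply 10.6.3. This agrees with the default in SAP 10.3.1, which treats an event of undeterminable phase as on-treatment, and with the eCRF-date footnotes.
- **If imputation is kept:** delete the exacerbation line in 10.6.3; define study treatment start date as the randomisation date for this rule; set the both-missing resolution to min(next onset - 1 day, treatment stop date), since a plain - 1 would fall a day short of treatment stop when the gap is the last one; and state that the 7-day merge uses recorded dates only.
- **In either case:** align SAP 7.3.2.2 with the Table 2.23 note and the EFF_T15 footnotes on whether undated events enter the annualised rate.

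The cost is SAP wording and the matching programming specification. Data collection, sample size and the primary analysis are untouched.

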## 10.7. Appendix 7: Abbreviations & Trade Marks

### 10.7.1. Abbreviations

Abbreviation	Description
ACT	Asthma Control Test
ADaM	Analysis Data Model
ADR	Adverse Drug Reaction
AE	Adverse Event
ANCOVA	Analysis of Covariance
A&R	Analysis and Reporting
ASUI	Asthma Symptom Utility Index
ATC	Anatomical Therapeutic Chemical
BMQ	Beliefs in Medicine Questionnaire
CDISC	Clinical Data Interchange Standards Consortium
CI	Confidence Interval
CIS	Connected Inhaler System
CS	Clinical Statistics
CSR	Clinical Study Report
DBF	Database Freeze
DBR	Database Release
DOB	Date of Birth
DP	Decimal Places
DM	Data Management
DPI	Dry powder inhaler
eCRF	Electronic Case Record Form
ER	Emergency Room
EW	Early Withdrawal
FeNO	Fractional exhaled Nitric Oxide
GLM	Generalized Linear Model
GSK	GlaxoSmithKline
HCP	Healthcare Professional
HCRU	Health Care Resource Utilization
IA	Interim Analysis
ICH	International Conference on Harmonization
ICF	Informed Consent Form
ICS	Inhaled Corticosteroid
IDSL	Integrated Data Standards Library
ITT	Intent-To-Treat
J2R	Jump to reference
LABA	Long-Acting Beta2-Agonist
MAR	Missing At Random
MARS-A	Medication Adherence Report Scale for Asthma
MDI	Metered dose inhaler
MMRM	Mixed Model Repeated Measures
PAM	Patient Activation Measure
PDMP	Protocol Deviation Management Plan
PEF	Peak Expiratory Flow
PRO	Patient Reported Outcomes
PT	Preferred Term

Abbreviation	Description
QC	Quality Control
RAP	Reporting & Analysis Plan
RFD	Rescue Free Day
RAMOS	Randomisation & Medication Ordering System
SAC	Statistical Analysis Complete
SAE	Serious Adverse Event
S&P	Statistics and Programming
SD	Standard Deviation
SDL	Source Data Lock
SDTM	Study Data Tabulation Model
SGRQ	St. Georges Respiratory Questionnaire
SI	System Independent
SMQ	Standardised MedDRA Queries
SOC	System Organ Class
TRU	Total Rescue Use
SOP	Standard Operation Procedure
TA	Therapeutic Area
TFL	Tables, Figures & Listings

### 10.7.2. Trademarks

Trademarks of the GlaxoSmithKline Group of Companies	Trademarks not owned by the GlaxoSmithKline Group of Companies
BREO	ACT
ELLIPTA	ASUI
RELVAR	BMQ

## 10.8. Appendix 8: List of Data Displays

### 10.8.1. Data Display Numbering

The following numbering will be applied for RAP generated displays:

Section	Tables	Figures
Study Population	1.01 to 1.44	1.01 to 1.02
Efficacy	2.01 to 2.41	2.01 to 2.22
Safety	3.01 to 3.29	None
Section	Listings	
ICH Listings	1 to 19	
Other Listings	20 to 44	

### 10.8.2. Mock Example Shell Referencing

Non IDSL specifications will be referenced as indicated and if required example mock-up displays provided in [Appendix 9: Example Mock Shells for Data Displays: Example Mock Shells for Data Displays](#).

Section	Figure	Table	Listing
Study Population	POP_Fn	POP_Tn	POP_Ln
Efficacy	EFF_Fn	EFF_Tn	EFF_Ln
Safety	Not applicable	SAFE_Tn	SAFE_Ln

**NOTES:**

- Non-Standard displays are indicated in the 'IDSL / Example Shell' or 'Programming Notes' column as '[Non-Standard] + Reference.'

### 10.8.3. Deliverables

Delivery [Priority] 	Description
SAC [2]	Final Statistical Analysis Complete
DRY RUN [1]	Dry Run

**NOTES:**

- Indicates priority (i.e. order) in which displays will be generated for the reporting effort

#### 10.8.4. Study Population Tables

Study Population Tables					
No.	Population	IDSL / Example Shell	Title	Programming Notes	Deliverable [Priority]
Subject Disposition					
1.1.	Screened	IDSL_SP1	Summary of Subject Populations	See Section 4 for population details	SAC [2] DRY RUN [1]
1.2.	Enrolled	IDSL_ES6	Summary of Screening Status and Reasons for Screen Failure		SAC [2] DRY RUN [1]
1.3.	Enrolled	IDSL_ES6	Summary of Run-in Status and Reasons for Run-In Failure		SAC [2] DRY RUN [1]
1.4.	ITT	POP_T1	Summary of Attendance at Each Visit	Note: Visit 2/3/4 subjects may be randomised or re-entered into run-in up 3 times if ACT $\geq$ 20. Note: Visits 6/7/8/9 are Healthcare Professional Dashboard reviews for Arm 1 and Arm 3 .	SAC [2] DRY RUN [1]
1.5.	ITT	IDSL_ES1	Summary of Subject Disposition for the Subject Conclusion Record		SAC [2] DRY RUN [1]
1.6.	ITT	IDSL_ES4	Summary of Subject Disposition at Each Study Epoch		SAC [2] DRY RUN [1]
1.7.	ITT	IDSL_SD1	Summary of Treatment Status and Reasons for Discontinuation of Study Treatment		SAC [2] DRY RUN [1]
1.8.	ITT	POP_T2	Summary of Relvar/Breo ELLIPTA Sensor Status		SAC [2] DRY RUN [1]

Study Population Tables					
No.	Population	IDSL / Example Shell	Title	Programming Notes	Deliverable [Priority]
1.9.	ITT	POP_T2	Summary of Salbutamol MDI Sensor Status		SAC [2] DRY RUN [1]
1.10.	ITT	POP_T3	Summary of App Status		SAC [2] DRY RUN [1]
1.11.	Enrolled	IDSL_NS1	Summary of Number of Subjects Enrolled by Country and Site ID	Disclosure display Add "No Treatment" column Do by page by country to help fit all columns in one width.	SAC [2] DRY RUN [1]
1.12.	ITT	IDSL_NS1	Summary of Number of Subjects Enrolled by Country and Site ID	Do by page by country for consistency with above display	SAC [2] DRY RUN [1]
1.13.	ITT	IDSL_IE1	Summary of Inclusion/Exclusion Criteria Deviations		SAC [2] DRY RUN [1]
1.14.	ITT	IDSL_DV1	Summary of Important Protocol Deviations		SAC [2] DRY RUN [1]
Demographic and Baseline Characteristics					
1.15.	ITT	IDSL_DM1	Summary of Demographic Characteristics	Include, Gender, Age (years), Age group categories: 18-64, 65-84 and >=85, Ethnicity, Height, Weight, BMI	SAC [2] DRY RUN [1]
1.16.	ITT	IDSL_DM1	Summary of Demographic Characteristics by Country		SAC [2] DRY RUN [1]
1.17.	Enrolled	IDSL_DM11	Summary of Age ranges	Disclosure displays / Categories: 18-64, 65-84 and >=85. Include "No Treatment" column	SAC [2] DRY RUN [1]

Study Population Tables					
No.	Population	IDSL / Example Shell	Title	Programming Notes	Deliverable [Priority]
1.18.	ITT	IDSL_DM5	Summary of Race and Racial Combinations		SAC [2] DRY RUN [1]
1.19.	ITT	IDSL_DM6	Summary of Race and Racial Combination Details		SAC [2] DRY RUN [1]
Medical Conditions					
1.20.	ITT	IDSL_MH4	Summary of Current Medical Conditions		SAC [2] DRY RUN [1]
1.21.	ITT	IDSL_MH4	Summary of Past Medical Conditions		SAC [2] DRY RUN [1]
1.22.	ITT	IDSL_FH1	Summary of Family History of Cardiovascular Risk Factors		SAC [2] DRY RUN [1]
1.23.	ITT	IDSL_SU1	Summary of Substance Use at Screening	Include Smoking History, for the Current and Former Smokers include Years smoked, Cigarettes/Day, Smoking Pack Years	SAC [2] DRY RUN [1]
Disease Characteristics					
1.24.	ITT	POP_T4	Summary of Asthma Duration at Screening		SAC [2] DRY RUN [1]
1.25.	ITT	POP_T5	Summary of Exacerbation History at Screening		SAC [2] DRY RUN [1]
1.26.	ITT	POP_T6	Summary of Screening and Randomisation Peak Expiratory Flow (PEF)	Summarize using the maximum value at visit	SAC [2] DRY RUN [1]

Study Population Tables					
No.	Population	IDSL / Example Shell	Title	Programming Notes	Deliverable [Priority]
1.27.	ITT	POP_T6	Summary of Screening and Randomisation Peak Expiratory Flow (PEF) by Country	Summarize using the maximum value at visit	SAC [2] DRY RUN [1]
1.28.	ITT	POP_T6	Summary of Screening and Randomisation Fractional Exhaled Nitric Oxide (FeNO)	Summarize using the maximum value at visit	SAC [2] DRY RUN [1]
Concomitant Medications					
1.29.	ITT	IDSL_CM1	Summary of Concomitant Medications Taken in the Run-in, Medications Given for Severe Exacerbation		SAC [2] DRY RUN [1]
1.30.	ITT	IDSL_CM1	Summary of On-Treatment Asthma Concomitant Medications, Medications Given for Severe Exacerbation		SAC [2] DRY RUN [1]
1.31.	ITT	IDSL_CM1	Summary of On-Treatment Asthma Concomitant Medications		SAC [2] DRY RUN [1]
1.32.	ITT	IDSL_CM1	Summary of Post-Treatment Asthma Concomitant Medications		SAC [2] DRY RUN [1]
1.33.	ITT	IDSL_CM1	Summary of Run-in Treatment Asthma Concomitant Medications		SAC [2] DRY RUN [1]
1.34.	ITT	IDSL_CM1	Summary of On-Treatment Non-Asthma Concomitant Medications		SAC [2] DRY RUN [1]
1.35.	ITT	IDSL_CM1	Summary of Post-Treatment Non-Asthma Concomitant Medications		SAC [2] DRY RUN [1]
1.36.	ITT	IDSL_CM1	Summary of Run-in Treatment Non-Asthma Concomitant Medications		SAC [2] DRY RUN [1]

Study Population Tables					
No.	Population	IDSL / Example Shell	Title	Programming Notes	Deliverable [Priority]
1.37.	ITT	IDSL_CM1	Summary of Asthma Concomitant Medications Taken Prior to Screening	Ensure the observations dates are pre-screening visit 1 (there is a specific prior conmeds page in eCRF	SAC [2] DRY RUN [1]
Exposure and Treatment Compliance					
1.38.	ITT	POP_T7	Summary of Exposure to Study Medication	Post-randomisation treatment exposure	SAC [2] DRY RUN [1]
1.39.	ITT	POP_T8	Summary of the Frequency of Puffs Per Day – ELLIPTA Sensor	Programming Note: Repeat for Months 2, 3, 4, 5, 6, Months 4-6, Months 1-6 and Months 1-3. Frequency of puffs per day over the baseline and on-treatment period as defined in the Assessment Windows of RAP	SAC [2] DRY RUN [1]
1.40.	ITT	POP_T8	Summary of the Frequency of Puffs Per Day – MDI Sensor	Programming Note: Repeat for Months 2, 3, 4, 5, 6, Months 4-6, Months 1-6 and Months 1-3. Frequency of puffs per day over the baseline and on-treatment period as defined in the Assessment Windows of RAP	SAC [2] DRY RUN [1]

Study Population Tables					
No.	Population	IDSL / Example Shell	Title	Programming Notes	Deliverable [Priority]
1.41.	ITT	POP_T9	Summary of Treatment Compliance	Post-randomisation compliance Note: Treatment compliance = (Total number of inhalation taken / Expected Inhalation x (Stop date - Start date + 1)) x 100 where Total Number of Inhalations Taken is the total number of doses taken from all inhalers, Expected Inhalations is equal to 1 and Start Date and Stop Date are the earliest treatment start date on or post randomisation and the latest treatment stop date recorded for all the inhalers.	SAC [2] DRY RUN [1]
Others					
1.42.	ITT	POP_T10	Summary of Incidence of Preferred Time of Dosing over the Treatment Period		SAC [2] DRY RUN [1]
1.43.	ITT	POP_T11	Summary of HCP Dashboard Review by Visit	Note: Visits 6/7/8/9 are Healthcare Professional Dashboard reviews for Arm 1 and Arm 3 [1] Action taken – Email/Text/Phone Contact	SAC [2] DRY RUN [1]
1.44.	ITT	POP_T12	Summary of Prior Prescription Details		SAC [2] DRY RUN [1]

### 10.8.5. Study Population Figures

Study Population Figures					
No.	Population	IDSL / Example Shell	Title	Programming Notes	Deliverable [Priority]
Relvar/Breo ELLIPTA Adherence					
1.1.	ITT	POP_F1	Frequency of ELLIPTA Puffs Per Day– ELLIPTA Sensor	Programming Note: Repeat for Period: Month 1, 2, 3, 4, 5, 6, Month 4-6, Month 1-3, Month 1-6.	SAC [2] DRY RUN [1]
1.2.	ITT	POP_F1	Frequency of MDI Puffs Per Day – MDI Sensor	Programming Note: Repeat for Period: Month 1, 2, 3, 4, 5, 6, Month 4-6, Month 1-3, Month 1-6.	SAC [2] DRY RUN [1]

### 10.8.6. Efficacy Tables

Efficacy Tables					
No.	Population	IDSL / Example Shell	Title	Programming Notes	Deliverable [Priority]
Relvar/Breo ELLIPTA Adherence					
2.1.	ITT	EFF_T1	Summary of Monthly Percentage of ELLIPTA doses taken (daily adherence) between the beginning of month 1 and the end of month 6 as determined by the maintenance sensor – Observed Data	Use the observed monthly values (month 1, 2, 3, 4, 5, 6) [1] Baseline adherence is calculated using up to the last 28 days of daily adherence data during the run-in period.	SAC [2] DRY RUN [1]

Efficacy Tables					
No.	Population	IDSL / Example Shell	Title	Programming Notes	Deliverable [Priority]
2.2.	ITT	EFF_T2	Summary of Statistical Analysis of Percentage of ELLIPTA doses taken (daily adherence) between the beginning of month 4 and the end of month 6 as determined by the maintenance sensor	Present comparisons Arm 1,2,3,4 v Arm 5	SAC [2] DRY RUN [1]
2.3.	ITT	EFF_T2	Summary of Statistical Analysis of Percentage of ELLIPTA doses taken (daily adherence) between the beginning of month 4 and the end of month 6 as determined by the maintenance sensor – Generalised Linear Model (Sensitivity Analysis)	Present comparisons Arm 1,2,3,4 v Arm 5	SAC [2]
2.4.	ITT	EFF_T3	Summary of Statistical Analysis of Percentage of ELLIPTA doses taken (daily adherence) between the beginning of month 4 and the end of month 6 as determined by the maintenance sensor by Baseline ACT Total Score Group	Subgroup analysis output Update footer with interaction between treatment group arm and baseline ACT Total Score Group	SAC [2] DRY RUN [1]
2.5.	ITT	EFF_T3	Summary of Statistical Analysis of Percentage of ELLIPTA doses taken (daily adherence) between the beginning of month 4 and the end of month 6 as determined by the maintenance sensor by Age Group	Subgroup analysis output Update footer with interaction between treatment group arm and baseline ACT Total Score Group	SAC [2] DRY RUN [1]
2.6.	ITT	EFF_T4	Summary of Statistical Analysis of Percentage of ELLIPTA doses taken (daily adherence) between the beginning of month 1 and the end of month 3 as determined by the maintenance sensor	Present comparisons Arms 1,2,3,4 v Arm 5	SAC [2] DRY RUN [1]
2.7.	ITT	EFF_T4	Summary of Statistical Analysis of Percentage of ELLIPTA doses taken (daily adherence) between the beginning of month 1 and the end of month 3 as determined by the maintenance sensor – Generalised Linear Model (Sensitivity Analysis)	Present comparisons Arm 1,2,3,4 v Arm 5	SAC [2]

Efficacy Tables					
No.	Population	IDSL / Example Shell	Title	Programming Notes	Deliverable [Priority]
2.8.	ITT	EFF_T4	Summary of Statistical Analysis of Percentage of ELLIPTA doses taken (daily adherence) between the beginning of month 1 and the end of month 6 as determined by the maintenance sensor	Present comparisons Arms 1,2,3,4 v Arm 5	SAC [2] DRY RUN [1]
2.9.	ITT	EFF_T4	Summary of Statistical Analysis of Percentage of ELLIPTA doses taken (daily adherence) between the beginning of month 1 and the end of month 6 as determined by the maintenance sensor – Generalised Linear Model (Sensitivity Analysis)	Present comparisons Arm 1,2,3,4 v Arm 5	SAC [2]
2.10.	ITT	EFF_T5	Summary of Statistical Analysis of Percentage of ELLIPTA doses taken (daily adherence) between the beginning of month 4 and the end of month 6 as determined by the maintenance sensor – Impact of Feedback of Sensor Data to HCP	Present comparisons Arm 1 v 2, Arm 3 v 4	SAC [2] DRY RUN [1]
2.11.	ITT	EFF_T6	Summary of Statistical Analysis of Percentage of ELLIPTA doses taken (daily adherence) between the beginning of month 4 and the end of month 6 as determined by the maintenance sensor – Impact of Feedback on Rescue Medication Use	Present comparisons Arm 1 v 3, Arm 2 v 4	SAC [2] DRY RUN [1]
Salbutamol MDI Rescue Medication Use					
2.12.	ITT	EFF_T1	Summary of Monthly Percentage of Rescue Free Days between the beginning of month 1 and then end of month 6 as determined by the rescue medication sensor – Observed Data	Use the observed monthly values (month 1, 2, 3, 4, 5, 6) [1] Baseline rescue free use is calculated using up to the last 28 days of daily rescue use data during the run-in period.	SAC [2] DRY RUN [1]
2.13.	ITT	EFF_T4	Summary of Statistical Analysis of Percentage of Rescue Free Days between the beginning of month 4 and the end of month 6 as determined by the maintenance sensor	Present comparisons Arms 1,2,3,4 v Arm 5	SAC [2] DRY RUN [1]

Efficacy Tables					
No.	Population	IDSL / Example Shell	Title	Programming Notes	Deliverable [Priority]
2.14.	ITT	EFF_T1	Summary of Total Rescue Medication Use as determined by the maintenance sensor		SAC [2] DRY RUN [1]
Asthma Control Test (ACT)					
2.15.	ITT	EFF_T1	Summary of Asthma Control Test (ACT) Total Score	Programming Note: Add screening visit score. [1] Baseline ACT total score is taken at Randomisation visit.	SAC [2] DRY RUN [1]
2.16.	ITT	EFF_T4	Summary of the Statistical Analysis of Change from Baseline (Randomisation) in ACT Total Score at Month 6		SAC [2] DRY RUN [1]
2.17.	ITT	EFF_T12	Summary of Percentage of Subjects Who Have Either an ACT Total Score $\geq 20$ and/ or $\geq 3$ Point Increase from Baseline in ACT Total Score	See SLS T2.1	SAC [2] DRY RUN [1]
2.18.	ITT	EFF_T13	Summary of the Statistical Analysis of Percentage of Patients Who Have an ACT Total Score of $\geq 20$ at Month 6		SAC [2] DRY RUN [1]
2.19.	ITT	EFF_T13	Summary of the Statistical Analysis of Percentage of Patients with an Increase from Baseline $\geq 3$ in ACT Total Score at Month 6		SAC [2] DRY RUN [1]
2.20.	ITT	EFF_T13	Summary of the Statistical Analysis of Percentage of Patients Who Have Either an ACT Total Score of $\geq 20$ and/or an Increase from Baseline of $\geq 3$ in ACT Total Score at Month 6		SAC [2] DRY RUN [1]
Unscheduled Health Care Utilisation					
2.21.	ITT	EFF_T14	Summary of Unscheduled Asthma Related Healthcare Utilisation During the Study		SAC [2] DRY RUN [1]
2.22.	ITT	EFF_T22	Summary of Primary Care Visits relating to HCP Dashboard Review		SAC [2] DRY RUN [1]

Efficacy Tables					
No.	Population	IDSL / Example Shell	Title	Programming Notes	Deliverable [Priority]
Severe On-treatment Exacerbations					
2.23.	ITT	EFF_T15	Summary of Severe On-Treatment and Post-Treatment Asthma Exacerbations	Exacerbation duration and rates will only be determined from those events that have dates of onset and resolution  Include a total column	SAC [2] DRY RUN [1]
Asthma Symptom Utility Index (ASUI)					
2.24.	ITT	EFF_T1	Summary of Asthma Symptom Utility Index (ASUI) Score	Programming Note: Add screening visit score. Decimal places need to be increased by 2 dp for all values. [1] Baseline ASUI total score is taken at Randomisation visit.	SAC [2] DRY RUN [1]
2.25.	ITT	EFF_T16	Summary of Statistical Analysis of Percentage of Patients Meeting a Responder Threshold of $\geq 0.09$ Points Improvement (Increase) from Baseline (Randomisation) for the ASUI Total Score at Visit 10 (Month 6)		SAC [2] DRY RUN [1]
2.26.	ITT	EFF_T4	Summary of Statistical Analysis of Change from Baseline (Randomisation) in Asthma Symptom Utility Index (ASUI) Score at Visit 10 (Month 6)		SAC [2] DRY RUN [1]
St. George's Respiratory Questionnaire (SGRQ)					
2.27.	ITT	EFF_T1	Summary of St. George's Respiratory Questionnaire (SGRQ) Total Score	Programming Note: Add screening visit score. [1] Baseline SGRQ total score is taken at Randomisation visit.	SAC [2] DRY RUN [1]

Efficacy Tables					
No.	Population	IDSL / Example Shell	Title	Programming Notes	Deliverable [Priority]
2.28.	ITT	EFF_T13	Statistical Analysis of Percentage of Patients Meeting a Responder Threshold of $\geq 4$ Points Improvement (Decrease) from Baseline (Randomisation) for the SGRQ Total Score at Visit 10 (Month 6)		SAC [2] DRY RUN [1]
2.29.	ITT	EFF_T4	Summary of Statistical Analysis of Change from Baseline (Randomisation) in St. George's Respiratory Questionnaire (SGRQ) at Visit 10 (Month 6)		SAC [2] DRY RUN [1]
Patient Activation Measure (PAM-13)					
2.30.	ITT	EFF_T1	Summary of Patient Activation Measure (PAM) 13 Total Score	Programming Note: Add randomisation visit score. [1] Baseline PAM-13 total score is taken at Screening visit.	SAC [2] DRY RUN [1]
Medication Adherence Rating Scale Asthma (MARS-A)					
2.31.	ITT	EFF_T1	Summary of Medication Adherence Report Scale-Asthma (MARS-A) Total Score	Programming Note: Add randomisation visit score. [1] Baseline MARS-A total score is taken at Screening visit.	SAC [2] DRY RUN [1]
Beliefs about Medicines (BMQ)					
2.32.	ITT	EFF_T1	Summary of BMQ General Benefit Total Score	Programming Note: Add randomisation visit score. [1] Baseline BMQ total score is taken at Screening visit.	SAC [2] DRY RUN [1]
2.33.	ITT	EFF_T1	Summary of BMQ General Harm Total Score	Programming Note: Add randomisation visit score. [1] Baseline BMQ total score is taken at Screening visit.	SAC [2] DRY RUN [1]

Efficacy Tables					
No.	Population	IDSL / Example Shell	Title	Programming Notes	Deliverable [Priority]
2.34.	ITT	EFF_T1	Summary of BMQ General Overuse Total Score	Programming Note: Add randomisation visit score. [1] Baseline BMQ total score is taken at Screening visit.	SAC [2] DRY RUN [1]
2.35.	ITT	EFF_T1	Summary of BMQ Specific Necessity Total Score	Programming Note: Add randomisation visit score. [1] Baseline BMQ total score is taken at Screening visit.	SAC [2] DRY RUN [1]
2.36.	ITT	EFF_T1	Summary of BMQ Specific Concern Total Score	Programming Note: Add randomisation visit score. [1] Baseline BMQ total score is taken at Screening visit.	SAC [2] DRY RUN [1]
Medical Device Incidents					
2.37.	ITT	EFF_T21	Summary of Medical Device Incidents (Sensors)		SAC [2] DRY RUN [1]
Fractional Exhaled Nitric Oxide (FeNO) and Peak Expiratory Flow (PEF)					
2.38.	ITT	EFF_T1	Summary of Fractional Exhaled Nitric Oxide (FeNO)	Programming Note: Add screening visit reading. [1] Baseline FeNO readings are taken at Randomisation visit.	SAC [2] DRY RUN [1]
2.39.	ITT	EFF_T23	Summary of Change from Baseline (Randomisation) in Fractional Exhaled Nitric Oxide (FeNO) at Month 6 (Visit 10) by Percentage of ELLIPTA doses taken (daily adherence) between the beginning of Month 4 and the end of Month 6 Group	The adherence observations should be those taken from the analysis dataset holding the observed % values. These should be grouped in quantiles using the 25th, 50th and 75th percentiles as the data group boundaries.	SAC [2] DRY RUN [1]

Efficacy Tables					
No.	Population	IDSL / Example Shell	Title	Programming Notes	Deliverable [Priority]
2.40.	ITT	EFF_T1	Summary of Peak Expiratory Flow (PEF)	Programming Note: Add screening visit reading. [1] Baseline FeNO readings are taken at Randomisation visit.	SAC [2] DRY RUN [1]
2.41.	ITT	EFF_T23	Summary of Change from Baseline (Randomisation) in Peak Expiratory Flow (PEF) at Month 6 (Visit 10) by Percentage of ELLIPTA doses taken (daily adherence) between the beginning of Month 4 and the end of Month 6 Group	The adherence observations should be those taken from the analysis dataset holding the observed % values. These should be grouped in quantiles using the 25th, 50th and 75th percentiles as the data group boundaries	SAC [2] DRY RUN [1]

